1.2. Schema

Figure 1: Schematic Overview of the Study*

G=group; IDMC=Independent Data Monitoring Committee; Rand=randomization; Vacc=vaccination; vp=virus particle

*Note: Study duration for participants in Part 1 is approximately 8 months (Groups 4-6) to 12 months (Groups 1-3) provided the intervals in the SoA are respected.

a. Dose Selection Cohort: 50 participants per group will receive 1 or 2 doses of the active vaccine.

Participants in Groups 1-3 will be given a booster vaccination as of 6 months after the last vaccination with active vaccine (Vaccination 1) and the booster dose level for these participants will be 2.5×10^{10} vp per 0.5 mL. Unblinding to the primary vaccination regimen will take place approximately 6 months after the first vaccination in Part 1.

1.3. Schedule of Activities (SoA)

1.3.1. Part 1: Dose Selection Cohort (Groups 1, 2 and 3) Booster 6 Months Post-dose 1 (SoA visits identical up to Visit 8 for all groups in Part 1)

Phase	Screening	Study Period												
Visit #	1	2	3	4	5	6	7	8	9	10	11	12	13	Exit ^b
Visit Timing ^a		Vac 1	Vac 1 + 7 d	Vac 1 + 28 d	Vac 1 + 56 d	Vac 2 + 7 d	Vac 2 + 14 d	Vac 2 + 28 d	Vac 1 + 6 m	Vac 3 + 7 d	Vac 3 + 14 d	Vac 3 + 28 d	Vac 3 + 6 m	
Target Visit Day ±Window	-28 to 1	1	8±2 ^c	29±3	57-3+/7	64*±2 ^c	71*±2	85*±3	Day 184+30 **	Day 191* ±2 ^c	Day 198*±3	Day 212*±3	Day 366* ±21	
Visit Type	Screening	Vaccination 1	Safety	Safety (and Immuno)	Vaccination 2	Safety	Safety (and Immuno)	Safety	Vaccination 3	Safety	Safety (and Immuno)	Safety	Safety (and Immuno)	Early Exit
Written informed consent/assent ^d	●													
Inclusion/exclusion criteria	●	● ¹												
Demographics	●													
Medical history/prestudy meds	●													
Physical examination ^e	●													
Pulse oximetry by site staff ^f		● ¹	●	●	● ¹	●	●	●	● ¹	●	●	●	●	
Distribution of pulse oximeter ^g		●												
Vital signs ^h incl. body temperature	●	● ²	●	●	● ²	●	●	●	● ²	●	●	●	●	● ⁴
Rapid Serological test for anti SARS CoV 2 antibody (local) ^{ij}	● ¹	● ¹												
Nasal swab (centrally)		●							●					
Randomization		● ¹							● ¹					
Pre vaccination check ^k		● ¹			● ¹				● ¹					
Urine pregnancy test ^l	●	● ¹			● ¹				● ¹					
Blood collection immunogenicity														
Humoral immunity (serum), 10 mL blood draw			● ¹		●	● ¹		●		● ¹		●	●	● ³

Phase	Screening	Study Period	3	4	5	6	7	8	At approximately 6 months of study participation	9	10	11	12	13	Exit ^b							
Visit #	1	2	Vac 1 + 7 d	Vac 1 + 28 d	Vac 1 + 56 d	Vac 2 + 7 d	Vac 2 + 14 d	Vac 2 + 28 d		Vac 1 + 6 m	Vac 3 + 7 d	Vac 3 + 14 d	Vac 3 + 28 d	Vac 3 + 6 m								
Visit Timing ^a		Vac 1																				
Target Visit Day ±Window	-28 to 1	1	8±2 ^c	29±3	57-3±7	64*±2 ^c	71*±2	85*±3		Day 184+30 **	Day 191* ±2 ^c	Day 198*±3	Day 212*±3	Day 366* ±21								
Visit Type	Screening	Vaccination 1	Safety	Safety (and immuno)	Vaccination 2	Safety	Safety (and Immuno)	Safety		Vaccination 3	Safety	Safety (and Immuno)	Safety	Safety (and Immuno)	Early Exit							
Blood collection coagulopathy																						
Clinical laboratory blood sample, 14 mL (whole blood/plasma/serum) ^m		● ¹		●	● ¹		●			● ¹		●										
Vaccination		●			●					●												
Post vaccination observation ⁿ		●			●					●												
Solicited AE recording		Continuous		Continuous						Continuous												
Unsolicited AE recording ^o		Continuous (Day 28)			Continuous (Day 28)						Continuous (Day 28)											
MAAE recording ^p										Continuous												
SAE/AESI recording ^q										Continuous												
Concomitant meds ^r										Continuous												
Participant reactogenicity diary dispensation and review ^s		●	●				●			●					● ⁴							
eCOA training and set up ^t		●																				
Nasal swab and saliva collection training ^u		●																				
Training on AESI symptoms		●																				
Distribution of rulers, thermometers, and SIC reference card		●																				
SIC, including body temperature of the participant (PROs to be completed by the participant in the eCOA) ^v		● ¹																				
(Suspected) COVID 19 surveillance (symptom check) ^w										Continuous												

Phase	Screening	Study Period	3	4	5	6	7	8	At approximately 6 months of study participation	9	10	11	12	13	Exit ^b
Visit #	1	2	3	4	5	6	7	8		Vac 1 + 7 d	Vac 1 + 28 d	Vac 1 + 56 d	Vac 2 + 7 d	Vac 2 + 14 d	Vac 2 + 28 d
Visit Timing ^a		Vac 1	Vac 1 + 7 d	Vac 1 + 28 d	Vac 1 + 56 d	Vac 2 + 7 d	Vac 2 + 14 d	Vac 2 + 28 d		Vac 1 + 6 m	Vac 3 + 7 d	Vac 3 + 14 d	Vac 3 + 28 d	Vac 3 + 6 m	
Target Visit Day ±Window	-28 to 1	1	8±2 ^c	29±3	57-3±7	64*±2 ^c	71*±2	85*±3		Day 184±30 **	Day 191* ±2 ^c	Day 198*±3	Day 212*±3	Day 366* ±21	
Visit Type	Screening	Vaccination 1	Safety	Safety (and immuno)	Vaccination 2	Safety	Safety (and Immuno)	Safety		Vaccination 3	Safety	Safety (and Immuno)	Safety	Safety (and Immuno)	
AESI reminder ^x		Daily for 30 days after vaccination		Daily for 30 days after vaccination				Daily for 30 days after vaccination							

●¹ pre-vaccination; ●² pre- and post-vaccination; ●³ blood samples for immunogenicity will only be taken if the early exit visit is at least 10 days after the previous immunogenicity blood draw; ●⁴ if within 7 days of the previous vaccination

*The timings of visits after the second and third vaccinations will be determined relative to the actual day of that vaccination, respectively.

** Participants in Groups 1-3 will be given a booster vaccination as of 6 months after the last vaccination with active vaccine (Vaccination 1). Participants who have become infected with SARS-CoV-2 during the study after primary vaccination regimen is completed, may receive a booster (3rd) vaccination with the Ad26.COV2.S vaccine, after they have recovered from the acute illness (refer to Section 1.3.3 Procedures for Participants With [Suspected] COVID-19 for definition of recovered) and according to local recommendations on immunization (if available) OR once 1 month has passed since recovery, based on the investigator's judgement.

- If allowed by local regulations, study visits may take place at the participant's home or other location in the event of ongoing SARS-CoV-2 transmission in the area of the participant. If possible and allowed per local regulation, visits can be performed by a phone call or a telemedicine contact. Except for the screening and vaccination visits, assessments scheduled for the other visits may also be performed by a trained health care professional (HCP), if allowed per local regulations.
- For those participants who are unable to continue participation in the study up to Visit 13, but for whom consent is not withdrawn, an early exit visit will be conducted as soon as possible. Participants who no longer wish to receive study vaccination (see Section 7.1) will be offered all safety and reactogenicity follow-up visits according to the current Schedule of Activities. Participants who wish to withdraw consent from participation in the study (see Section 7.2) will be offered an optional visit for safety follow-up. This includes the safety assessments of the early exit visit (no blood sampling for immunogenicity).
- If a participant comes in early for Visit 3, or 6 ie, 1 to 2 days prior to the Target Visit Day per the allowed visit window, a subsequent phone call will be made at the end of the reactogenicity diary period to review reactogenicity diary information recorded between the actual visit and the end of the reactogenicity diary period.
- Signing of the ICF/assent should be done before any study-related activity.
- A full physical examination, including length/height, body weight will be carried out at screening. At other visits, an abbreviated, symptom-directed examination will be performed if determined necessary by the investigator.
- Pulse oximetry at Day 1 is mandatory, at all other visits only if applicable.
- Adolescent (12 to 17 years of age) participants will be provided a pulse oximeter at baseline to measure blood oxygen saturation and pulse rate during a COVID-19 episode (see Section 1.3.3).

- h. Pulse/heart rate, preferably supine systolic and diastolic blood pressure, respiratory rate, and body temperature. Pulse/heart rate measurements should be taken preceded by at least 5 minutes of rest (if feasible) in a quiet setting without distractions (eg, television, cell phones). Vital signs measurements are recommended before blood sampling. Body temperature will be measured preferably orally (routes to be recorded in the eCOA).
- i. Rapid serological test for anti-SARS-CoV-2 antibody will collect blood from a small puncture in the finger (finger-prick test at screening).
- j. If a rapid serologic test is completed ≤ 3 days before vaccination, a repeat test is not required on Day 1
- k. Investigator must check for clinically significant acute illness or body temperature $\geq 38.0^{\circ}\text{C}/100.4^{\circ}\text{F}$ at the time of vaccination. If any of these events occur at the scheduled time for vaccination, the vaccination can be rescheduled as long as this is in agreement with the allowed windows. If the vaccination visit cannot be rescheduled within the allowed window or the contraindications to vaccination persist, the sponsor should be contacted for further guidance. The investigator should also check if any other reasons, as listed in Section 7.1, have been met and would prevent further study vaccination.
- l. For participant of childbearing potential only.
- m. Whole blood samples will be used for complete blood cell count, including platelet count (hematology, see Section 10.2, Appendix 2), in a local laboratory or substitute for local laboratory, depending on local feasibility towards turnaround time of sample processing. Results should be available within 72 hours. The division of volumes between whole blood, plasma and serum is described in the laboratory manual. Serum and plasma are to be stored centrally for future testing to evaluate the impact of any potential thromboembolic events. Samples can also be tested (centrally) for anti-PF4 antibodies and platelet activation assay (if HIT/PF4 is positive). Unused samples may be used for immunogenicity testing.
- n. After each vaccination, participants will remain under observation at the study site for at least 30 minutes (or longer if required by institutional/local practice) for the presence of any acute reactions and solicited events. Any solicited local (at injection site) and systemic AEs, unsolicited AEs, SAEs, concomitant medications, and vital signs will be documented by study-site personnel following this observation period and participants will be allowed to leave the study site after it is documented that the required minimum post-vaccination observation period is complete.
- o. Adverse events and special reporting situations that are related to study procedures or that are related to non-investigational sponsor products will be reported from the time a signed and dated ICF is obtained until the end of the study/early withdrawal. All other unsolicited AEs and special reporting situations will be reported for each vaccination from the time of vaccination until 28 days post-vaccination.
- p. MAAEs are to be reported for all participants from the moment of the first vaccination until 6 months after vaccination, except for MAAEs leading to study discontinuation which are to be reported during the entire study. New onset of chronic diseases will be collected as part of the MAAEs.
- q. All SAEs and AESIs related to study procedures or non-investigational sponsor products will be reported from the time a signed and dated ICF is obtained until the end of the study/early withdrawal. All other SAEs and AESIs are to be reported from the moment of vaccination until completion of the participant's last study-related procedure.

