1. PROTOCOL SUMMARY

1.1. Synopsis

A Randomized, Observer-blind, Phase 2 Study to Evaluate the Safety, Reactogenicity, and Immunogenicity of Different Dose Levels of Ad26.COV2.S Administered as a One- or Two-dose Regimen in Healthy Adolescents From 12 to 17 Years Inclusive

Ad26.COV2.S (also known as Ad26COVS1, VAC31518, JNJ-78436735) is a monovalent vaccine composed of a recombinant, replication-incompetent human Ad26 vector, constructed to encode the SARS-CoV-2 spike (S) protein, stabilized in its prefusion conformation.

The term “adolescents” in this study refers to participants from 12 to 17 years of age inclusive.

OBJECTIVES AND ENDPOINTS

Part 1 Primary Objectives and Endpoints

Objectives	Endpoints
Primary	

 To assess the safety and reactogenicity of Ad26.COV2.S administered intramuscularly (IM) as a 1-dose regimen (at 2.5×10^{10} vp per 0.25 mL, 1.25×10^{10} vp, and 0.625×10^{10} vp dose level) or as a 2-dose (56-day interval) regimen (2.5×10^{10} vp per 0.5 mL, 1.25×10^{10} vp, and 0.625×10^{10} vp dose levels) in adolescents. 	
 Solicited local and systemic adverse events (AEs) for 7 days post-dose 1 and 2. Unsolicited AEs for 28 days post-dose 1 and 2. Medically-attended adverse events (MAAEs) from the first vaccination until 6 months post-dose 1 or post-dose 2. MAAEs leading to discontinuation will be collected during the entire study. Serious adverse events (SAEs) from the first vaccination until the end of the study. Adverse events of special interest (AESIs) from first vaccination until end of the study (incl multisystem inflammatory syndrome in children [MIS-C]).

 To assess the humoral immune response of Ad26.COV2.S administered IM as a 1-dose regimen (at 2.5×10^{10} vp per 0.25 mL, 1.25×10^{10} vp, and 0.625×10^{10} vp dose level) or as a 2-dose (56-day interval) regimen (2.5×10^{10} vp per 0.5 mL, 1.25×10^{10} vp, and 0.625×10^{10} vp dose levels) in adolescents. 	
 Serological response to vaccination as measured by spike-enzyme-linked immunosorbent assay (S-ELISA) (ELISA; Units/mL [EU/mL]) or equivalent assay, or virus neutralization assay (VNA) titers at 28 days post-dose 1 and 14 days post-dose 2.

Part 1 Secondary and Exploratory Objectives and Endpoints

Secondary	

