a Not more than 70% of males or females should be randomized in each age group.

b All participants must be seronegative for SARS CoV 2 antibodies at baseline (by finger prick test).

c Approximately 30% of participants should be between 16 to 17 years age and approximately 70% should be between 12 to 15 years of age.

d Participants in Groups 1-3 will be given a booster vaccination as of 6 months after the last vaccination with active vaccine (Vaccination 1) and the booster dose level for these participants will be 2.5 × 10¹⁰ vp per 0.5 mL.

Study Duration

The study duration from screening until the last follow-up visit will be, excluding the 28-day screening phase, approximately 8 months (Groups 4-6) to 12 months (Groups 1-3) provided the intervals in the SoA are respected, consisting of:

- Groups 1-3: ~12-month study duration comprising a 6-month study period including vaccination with 1 active dose and a placebo vaccination (56-day interval), followed by a booster vaccination at 6 months and follow-up (safety and immunogenicity) until at least 6 months after booster vaccination.
- Groups 4-6: ~8-month study duration comprising 2 active doses (56-day interval) and follow-up (safety and immunogenicity) until at least 6 months after second vaccination.

If a participant is unable to complete the study, but has not withdrawn consent, an early exit visit will be conducted. The end of study is considered as the last visit for the last participant in the study.

Study Procedures

For each group, safety will be assessed by collection of solicited local (at injection site) and systemic AEs, unsolicited AEs, MAAEs, SAEs, and AESIs. Other safety assessments include vital signs measurements (heart rate, preferably supine systolic and diastolic blood pressure, respiratory rate, and body temperature) and physical examinations at the time points indicated in Section 1.3, Schedule of Activities.

After each vaccination, participants will remain under observation at the study site for at least 30 minutes (or longer if required by institutional/local practice) for presence of any acute reactions and solicited events. Any solicited local or systemic AEs, unsolicited AEs, SAEs, AESIs, concomitant medications, and vital signs will be documented by study-site personnel following this observation period, and participants will be allowed to leave the study site after it is

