Solicited AEs, collected through a reactogenicity diary as part of the eCOA, will be recorded for each vaccination from the time of vaccination until 7 days post-vaccination.

All other unsolicited AEs and special reporting situations, whether serious or non-serious, will be reported for each vaccination from the time of vaccination until 28 days post-vaccination. Unsolicited AEs with the onset date outside the timeframe defined above (>28 days after previous study vaccination), which are ongoing on the day of the subsequent vaccination, should be recorded as such.

All SAEs and AEs leading to discontinuation from the study/vaccination (regardless of the causal relationship) are to be reported for all participants from the moment of first vaccination until completion of the participant's last study-related procedure, which may include contact for safety follow-up. The sponsor will evaluate any safety information that is spontaneously reported by an investigator beyond the time frame specified in the protocol.

MAAEs are defined as AEs with medically-attended visits including hospital, emergency department, urgent care clinic, or other visits to or from medical personnel for any reason. Routine study visits will not be considered medically-attended visits. New onset of chronic diseases will be collected as part of the MAAEs. MAAEs are to be reported for all participants from the first vaccination until 6 months after each vaccination, except for MAAEs leading to study discontinuation which are to be reported during the entire study.

To enable prompt response to a situation that could trigger pausing rules, the investigator should notify the sponsor's medical monitor or designee (AND fax or email the SAE form to Global Medical Safety Operations, if applicable), immediately and no later than 24 hours after becoming aware of any related AE of Grade 3 or above AND update the eCRF with relevant information on the same day the AE information is collected as described in Section [6.8](#).

All AEs will be followed until resolution or until clinically stable.

Adverse Events of Special Interest

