5.4. Primary Endpoints Analysis

5.4.1. Definition of Endpoint(s)

Safety and Reactogenicity Endpoints

Section [5.7.1](#) provides AE definitions associated with primary and secondary safety and reactogenicity endpoints.

The primary endpoints to assess the safety and reactogenicity are:

- Solicited local and systemic AEs for 7 days post-dose 1 and 2.
- Unsolicited AEs for 28 days post-dose 1 and 2.
- MAAEs from the first vaccination until 6 months post-last dose.
- SAEs, AESIs (TTS and MIS-C) and MAAEs leading to discontinuation from the first vaccination until the end of the study.

Humoral Immune Response Endpoints

S-ELISA (or equivalent assay, e.g. MSD) or VNA will be used as primary humoral immune response endpoint to assess the serological response to vaccination in Part 1:

- Serological response to vaccination as measured by S-ELISA (ELISA Units/mL [EU/mL]) or equivalent assay, or VNA titers at 28 days post-dose 1, and 14 days post-dose 2.

For S-ELISA or equivalent assay (e.g. MSD), wild type, and pseudovirion VNA, a sample is defined as positive if its value is strictly greater than the LLOQ (>LLOQ).

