5.7.1. Adverse Events

5.7.1.1. Definitions

Solicited AEs are used to assess the reactogenicity of the study vaccine and are predefined local events (pain/tenderness, erythema, and swelling at the injection site) and systemic events (fatigue, headache, nausea, and myalgia, fever) for which the participant or parent(s)/caregiver(s) is specifically questioned, and which are noted by participants or parent(s)/caregiver(s) in their reactogenicity diary. Unsolicited AEs are all AEs for which the participant or parent(s)/caregiver(s) is not specifically questioned.

MAAEs are defined as AEs with medically-attended visits including hospital, emergency room, urgent care clinic, or other visits to or from medical personnel for any reason. Routine study visits will not be considered medically-attended visits. New onset of chronic diseases will be collected as part of the MAAEs. MAAEs are to be reported for all participants from the first vaccination until 6 months after each vaccination, except for MAAEs leading to study discontinuation which are to be reported during the entire study.

Solicited AEs shown in the tables are extracted from the investigator assessment pages (CE) of the CRF. Solicited administration site symptoms will by definition be considered as related to the study vaccine.

The following adverse events of special interest (AESI) will be collected in this study:

- Thrombosis with Thrombocytopenia Syndrome (TTS), defined as:
 - Thrombotic events: suspected deep vessel venous or arterial thrombotic events as detailed in CTP Section 10.14 and in Section [6.10](#)
 - Thrombocytopenia, defined as platelet count below 150,000/ μ L.
- Multisystem Inflammatory Syndrome in Children (MIS-C), defined as:
 - An individual aged <21 years presenting with fever^a, laboratory evidence of inflammation^b, and evidence of clinically severe illness requiring hospitalization, with multisystem (≥ 2)

^a Fever $>38.0^{\circ}\text{C}$ for ≥ 24 hours, or report of subjective fever lasting ≥ 24 hours.

^b Including, but not limited to, one or more of the following: an elevated C-reactive protein (CRP), erythrocyte sedimentation rate (ESR), fibrinogen, procalcitonin, D-dimer, ferritin, lactic acid dehydrogenase (LDH), or interleukin 6 (IL-6), elevated neutrophils, reduced lymphocytes, and low albumin.

- organ involvement (cardiac, renal, respiratory, hematologic, gastrointestinal, dermatologic, or neurological); AND
- No alternative plausible diagnoses; AND

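### In Groups 4-6 the last visit may fall up to 21 days before the primary 6-month MAAE window closes, with no later contact scheduled

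*Protocol*

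**What the plan says.** **Endpoints and collection.** The Synopsis and Section 3 list among the primary endpoints "Unsolicited AEs for 28 days post-dose 1 and 2" and MAAEs up to 6 months after the dose. Section 8.3.1 states that "MAAEs are to be reported for all participants from the first vaccination until 6 months after each vaccination", and SAP 5.4.1 gives the endpoint as "MAAEs from the first vaccination until 6 months post-last dose". Footnote o of the Schedule of Activities (SoA) adds: "All other unsolicited AEs and special reporting situations will be reported for each vaccination from the time of vaccination until 28 days post-vaccination".

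**Follow-up promised.** Section 4.1 gives Groups 4-6 "follow-up (safety and immunogenicity) until at least 6 months after second vaccination" and gives Groups 1-3 the equivalent after the booster. Inclusion criterion 1.2 asks for contact up to the same point.

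**Visit windows (SoA 1.3.1 and 1.3.2).** Most are two-sided: Visit 4 at Day 29±3, Visit 8 at Day 85±3, Visit 10 at Day 191±2, Visit 12 at Day 212±3, Visit 13 at Day 366±21, and Visit 9 in Groups 4-6 at Day 240±21. Visit 9 in Groups 1-3 is Day 184+30. Under Section 4.4, attending the 6-month visit completes the study.

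**Catch-up call.** Footnote c opens "If a participant comes in early for Visit 3, or 6 ie, 1 to 2 days prior to the Target Visit Day" and, for that case, provides that "a subsequent phone call will be made at the end of the reactogenicity diary period to review reactogenicity diary information". Superscript c also stands on Visit 10, which the footnote text does not name.

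**Analysis.** SAP Table 3 ends Follow-up 2 at dose 2 plus 6 months and cuts it at last contact only for early discontinuation. SAP 5.7.1.5 counts a participant with no report as having no event. SAP 5.7.1.1 says: "Solicited AEs shown in the tables are extracted from the investigator assessment pages (CE) of the CRF".

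**The concern.** A safety endpoint defined over a fixed period needs a contact at or after the end of that period. In Groups 4-6 the SoA lets the last contact fall before the MAAE period ends, which conflicts with Section 4.1. The participant is still a completer, so the SAP keeps the full 6-month period and the unobserved days count as event-free. The error runs in one direction, towards fewer events, and the tables would not show it.

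Footnote c shows that the sponsor saw this problem for the diary. The same protection was not extended to the visits that close the 28-day and 6-month windows, and the footnote text missed Visit 10.

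**Working it through.** **1. The plan's own figures.** Taking 6 months as 183 days (an assumption that matches the SoA), the target days reproduce: 1+28=29, 57+28=85, 1+183=184, 57+183=240, 184+28=212. Visit 13 is the exception: 366=184+182, so its target is already one day short of 183. As a yardstick for size, exact Clopper-Pearson 90% limits for n=50 reproduce protocol Table 4: (0, 5.8%) at 0% and (37.6%, 62.4%) at 50%, widths 5.8 and 24.8 points.

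**2. Earliest permitted visit against window close.** Shortfall = closing day minus earliest day, with vaccinations on Days 1, 57 and 184.

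| Visit | Window closes | Earliest day | Days after dose | Shortfall | Next scheduled visit |
|---|---|---|---|---|---|
| 4 | Day 29 | 26 | 25 | 3 of 28 (10.7%) | Visit 5, Day 54-64 |
| 8 | Day 85 | 82 | 25 | 3 of 28 (10.7%) | Visit 9 |
| 9, Groups 1-3 | Day 184 | 184 | 183 | 0 | Visits 10-13 if boosted |
| 9, Groups 4-6 | Day 240 | 219 | 162 | 21 of 183 (11.5%) | none |
| 10 (diary) | Day 191 | 189 | 5 | 2 days | Visit 11, Day 195-201 |
| 12 | Day 212 | 209 | 25 | 3 of 28 (10.7%) | Visit 13 |
| 13 | Day 367 | 345 | 161 | 22 of 183 (12.0%) | none |

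Against its own Day 366 target, Visit 13 is 21 days short.

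**3. Gap after an early Visit 8 (Day 82).** In Groups 1-3 the next scheduled visit comes 184-82=102 to 214-82=132 days later. In Groups 4-6 it comes 219-82=137 to 261-82=179 days later. The primary analysis and the second IDMC analysis use data to 28 days post-dose 2, so for recently enrolled participants Visit 9 may come too late for those cuts.

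**4. Upper bound on lost MAAEs, Groups 4-6.** The documents give no MAAE risk, so a true 6-month risk p of 5% to 40% is assumed, with constant hazard and every participant seen on Day 219. Observed risk = 1-(1-p)^(162/183). Expected loss per group of 50 = 50 × (p - observed).

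| Assumed p | Observed | Lost per 50 |
|---|---|---|
| 5% | 4.44% | 0.28 |
| 10% | 8.91% | 0.55 |
| 20% | 17.93% | 1.04 |
| 40% | 36.38% | 1.81 |

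**5. Upper bound for the 28-day window after dose 2.** The same method with exponent 25/28, and nothing recovered later, gives 0.26, 0.51, 0.97 and 1.69 per 50.

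**The case against.** The strongest case for the plan is that collection does not depend on visits alone. MAAE recording is continuous, reporting to 6 months is required, and participants agree at entry to stay in contact that long. The eCOA asks daily for 30 days after each vaccination about symptoms that could point to TTS or MIS-C, and throughout the study about concerns that may need emergency care. Section 8 tells sites to use the window only when they must. The study tests no hypothesis, and the expected loss is small beside a confidence interval up to 24.8 points wide.

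Most of this stands, and it limits the size of the point. It does not close the gap. Neither eCOA question is a general AE or MAAE query, Section 8.3.2 prefers verbal questioning, and no contact is scheduled after the final visit.

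A reader might infer more than the documents support:

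- **That 28-day AE counts are cut off at Visits 4, 8 and 12.** They are not. Each is followed by another visit, and an event with onset by day 28 remains reportable when learned later.
- **That Groups 1-3 lose part of the primary MAAE window after dose 1.** Visit 9 is not due before Day 184, and Visits 10-13 follow in boosted participants. Their Visit 13 shortfall concerns the booster MAAE endpoint, which is secondary.
- **That the last diary days after an early Visit 10 are lost.** Entries are electronic, and Section 8 allows a diary to be reviewed at the following visit, here Visit 11.
- **That about half of participants exit early.** An even spread over ±21 days would give 21/43=49% early and a mean loss of 231/43=5.4 days. Section 8 asks for attendance on the planned day, so that spread is not a fair expectation.

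**Conclusion.** The point holds in a limited form. For Groups 4-6, SoA 1.3.2 contradicts Section 4.1 and allows up to 21 of about 183 days of a primary endpoint to go unobserved, with the SAP counting those days as event-free. The MAAE proportion can only be lowered. The worst-case loss is under 2 participants with an event per group of 50 (1.81/50=3.6 percentage points at an assumed 40% risk), and actual attendance should make it smaller.

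An early Visit 8 leaves up to 3 of 28 days unqueried at the primary and second IDMC analyses, and those days are later covered only by recall at Visit 9. Visit 10 has a real mismatch between superscript and footnote text, with a delayed diary review as the consequence. SAE and AESI endpoints run to the end of study, so an early last visit shortens their follow-up without breaking their definition.

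Day 240 lacks the asterisk that marks the other post-dose-2 visits. A reader might therefore treat it as a fixed study day, which with dose 2 on Day 64 would leave 219-64=155 days, a shortfall of 28 (15.3%). The SoA note and Section 8 time post-vaccination visits from the actual vaccination, so that reading is not supported.

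These sizes rest on 183 days for 6 months, constant hazard and assumed risks. No sample-size figure depends on them.

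**What to change.** Reconcile SoA 1.3.1 and 1.3.2 (windows and footnote c) with Sections 4.1 and 8.3.1:

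1. Set the final visits (Visit 9 in Groups 4-6, Visit 13 in Groups 1-3) no earlier than the actual last active vaccination plus 6 months, for example with a +21-day window only. This matches the period ends in SAP Table 3 and corrects the 182-day target of Visit 13. Alternatively, keep the windows and require an MAAE/SAE call at 6 months for anyone seen early.
2. Require an AE call at day 28 when Visit 8 or 12 is early.
3. Name Visit 10 in footnote c, and add the asterisk to Day 240.

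The cost is a narrower scheduling window or one phone call per participant seen early. With a late-only window, final immunogenicity samples move slightly later. Up to 21 days late is still inside the ±30 days that SAP 5.1.4 allows for samples planned more than 3 months after the last vaccination. No extra samples or participants are needed.
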